#### **Analysis methods**

No missing data imputation will be performed. Patients with missing data at one or both time points will not be included in the analysis. A one-way Repeated Measures Analysis of Variance (ANOVA) will be used to compare the differences between pre and post-baseline ARR if the data is normally distributed. The two-tailed test hypothesis for the primary outcome is H0: ARR mean difference between pre and post-baseline ARR is 0 vs H1: ARR mean difference between pre and post-baseline is different than 0. Statistical significance will be assessed at the 5% level.

In case the data is not normally distributed, Wilcoxon signed-rank test will be used instead. The Shapiro-Wilk test will be used to test for data normality.

Main primary outcome table will include only summary statistics for pre-baseline and post-baseline ARR data including the p-value for the statistical test result described above. Additionally, a table includes ARR summary statistics by visit, including ARR at each visit and absolute and relative change from baseline. For a change from baseline, 95% CIs for the difference will be presented together with summary statistics. These CIs will be included as a descriptive measure of effect and no inferences will be made.

## 14.1.2 Sensitivity Analyses of the Primary Outcome ARR

A sensitivity analysis will be conducted using two different methods for missing data imputation, to assess the robustness of the primary analysis described above.

The first method will include a Last Observation Carried Forward (LOCF) approach, for which the last available ARR from previous visits will be used for the analysis.

The second method will include a Baseline Observation Carried Forward (BOCF) for which missing data for post-baseline ARR will be imputed as the pre-baseline ARR.

Both summary statistics and statistical results will be presented in the same table as the primary analysis. These sensitivity analyses are considered as supportive of the primary analysis.

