9.2 Setting

9.2.1 Study Population

The study population will be identified according to the below inclusion and exclusion criteria. For inclusion in the study, all of the following inclusion criteria must be fulfilled:

- Patients must voluntarily give written informed consent. Patients must read and fully understand the Informed Consent Form (ICF)
 - 2. Adult patients, males or females patients ≥ 18 years old.
 - Patients with confirmed diagnosis of Relapsing-Remitting Multiple Sclerosis (RRMS) diagnosed by the treating physician according to applicable clinical practice guidelines – (currently McDonald 2017 criteria), with high disease activity.

as at least 1 point in the EDSS score or an increase of at least 1.5 points if the baseline EDSS score is 0. Disability Improvement is defined as improvement on ≥ 1 of 3 components (EDSS, T25FW, and/or 9HPT) confirmed ≥ 24 weeks apart and with a $\ge 20\%$ minimum threshold change for T25FW and 9HPT. Improvement on EDSS is defined as a decrease in EDSS by at least 1 point (1.5 points if baseline EDSS was 1.5). T25FW and 9HPT are optional and will be performed if done as per routine practice.

- 4. Patients should have been treated with the same first-line DMD (Interferons, Glatiramer Acetate, Teriflunomide, DMF) and at a stable dose for at least one year prior to switch to Cladribine tablets and should have been prescribed Cladribine tablets, according to the decision of the treating physician, prior to enrollment in the study. Any washout period and/or washout methods required before switching (such as elimination of Teriflunomide) must have been conducted, according to the decision of the treating physician.
- 5. Required history data should be available:
 - MS data for the 12-months pre-baseline period (annualized relapse rate)
 - MS Medication History (prior DMDs)
- Fulfilment of the criteria for treatment with Cladribine tablets per standard of care in accordance with the local SmPC

Patients are not eligible for this study if they fulfill any of the following exclusion criteria:

- 1. Contraindications to use of cladribine tablets according to the Summary of Product Characteristics
- Patients with history of alcohol or drug abuse that could potentially interfere with their participation in the study.
- 3. Patient that have received Cladribine in the past
- Concurrent participation in an investigational study in which patient assessment and/or treatment may be dictated by a protocol.

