## **9** General Specifications for Data Analyses

This section describes any general specifications not included in subsequent sections. This study is a single cohort study and no comparison between groups is planned. The "start date" for this study is the start date of treatment with Cladribine.

Continuous variables will be summarized using descriptive statistics, i.e. the number of patients with non-missing values (n), the number of patients with missing values (nmiss), mean, standard deviation (SD), median, 25th percentile (Q1) and 75th percentile (Q3), minimum, and maximum. If there are no missing values, the number of patients with missing values (nmiss) should be indicated by a 0. Mean, median, Q1, Q3, minimum and maximum will be reported with the same number of decimal places as collected in raw data while SD will be reported with one extra decimal place.

Qualitative variables will be summarized by frequency counts and percentages. Unless otherwise stated the calculation of proportions will be based on the number of patients of the analysis set of interest. Therefore, counts of missing observations will be included in the denominator and presented as a separate category.

The overall significance level is 5% two-sided. Confirmatory statistical tests will be performed on the primary outcome only. All other statistical tests mentioned in this IAP are to be regarded as exploratory. Exploratory statistical tests comparing study treatment groups will be performed two-sided. If confidence intervals (CIs) are to be calculated, these will be two-sided with a confidence probability of 95%, unless otherwise specified in this IAP.

In order to provide overall estimates of treatment effects, data will be pooled across sites. The "site" factor will not be considered in statistical models or for subgroup analyses due to the high number of participating sites in contrast to the anticipated small number of patients treated at each site.

All analyses will be performed using SAS® Software version 9.4 or higher. R version 3.2.2 or higher may be used to create some of the figures in case it provides a better alternative layout.

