# 14.1.1 Primary Objective: Derivation and analysis of the Primary Outcome ARR

#### **Derivations**

Pre-baseline ARR will be defined as a total number of relapses reported in the last 12 months prior to Cladribine treatment as collected in the "12 Month Historical MS Data".

Twelve month period before the End of Study follow-up (2 years) ARR will be calculated as the sum of the number of MS relapses reported at Visit 3 and Visit 4 divided by the number of days between Visit 4 date and Visit 2 date and multiplied by 365.25. If a patient discontinues the study prior to Visit 4, it will be set to missing and excluded from the primary analysis.

For other study visits, ARR will be calculated similarly including data from the last 2 visits, except for ARR at Visit 1 for which only the last 6-month data will be included, and the annualized rate will be adjusted as per the formula described above. For ARR at Visit 1 and Visit 2, Cladribine start date will be used as the date to calculate the number of days elapsed.

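### The BOCF test result in SAP 14.1.2 carries no evidence on drop-out: imputed differences are exactly zero, so its p-value repeats, or nearly repeats, the completers-only one

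*SAP*

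**What the plan says.** SAP 14.1.1 defines the two values that are compared. For the first, "Pre-baseline ARR will be defined as a total number of relapses reported in the last 12 months prior to Cladribine treatment". The second is the relapse count from Visits 3 and 4, annualised by the days between Visit 2 and Visit 4. For leavers, "If a patient discontinues the study prior to Visit 4, it will be set to missing and excluded from the primary analysis".

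The test depends on a Shapiro-Wilk result. With normal data, "A one-way Repeated Measures Analysis of Variance (ANOVA) will be used to compare the differences between pre and post-baseline ARR". Otherwise, "In case the data is not normally distributed, Wilcoxon signed-rank test will be used instead". SAP 9 adds: "The overall significance level is 5% two-sided". It makes the primary outcome the only confirmatory test.

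SAP 14.1.2 then plans two imputation methods to judge how robust that result is. LOCF carries forward the last ARR available from an earlier visit. The other method is "Baseline Observation Carried Forward (BOCF) for which missing data for post-baseline ARR will be imputed as the pre-baseline ARR". On reporting: "Both summary statistics and statistical results will be presented in the same table as the primary analysis". Both analyses are described in advance as supportive. The section does not say how the signed-rank test treats zero differences, or what result would count against robustness.

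Under Protocol 9.2.5 a patient who changes to another DMD is withdrawn. SAP 9.6 lists that change among the reasons for loss to follow-up.

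**The concern.** BOCF is commonly read as a cautious assumption, because a leaver is given no benefit. A reader who sees a BOCF p-value beside the primary p-value, and finds that they agree, will take this as evidence that drop-out did little harm. That holds only if the leavers can influence the second p-value. Here they have no influence on it under the usual zero rule, and almost none under ANOVA.

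Leavers include patients withdrawn because they changed DMD, which is plausibly related to relapse. The missing outcomes may therefore be the worse ones, and that is the situation a drop-out check should be able to expose.

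**Working it through.** **Inputs from the documents.** Planned enrolment N = 242 (Protocol 9.5); two-sided 5% level (SAP 9); tests and derivations as in SAP 14.1.1; BOCF as in SAP 14.1.2. Pre-baseline relapse history is required by inclusion criterion 5 (Protocol 9.2.1), so BOCF can be applied to every leaver. The plan gives no figure for the BOCF analysis. The assumptions behind 242 are blacked out, so there is no plan figure to reproduce. All rates and missing shares below are assumptions.

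**1. Signed-rank branch.** For a leaver, d = post − pre = pre − pre = 0. With zeros dropped, only completers with d ≠ 0 are ranked. Statistic, effective n and p-value are those of the completers-only test. This needs no assumption about rates. As confirmation, gamma-Poisson counts were simulated with N = 242: pre/post rates 1.2/0.2, 0.6/0.5 and 0.6/0.47, 10 to 40% missing, 12 scenarios of 1,500 runs. The two p-values were equal in 100% of runs. In one data set generated at 0.6/0.45 with 10% missing, p = 0.0371 in both.

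**2. Which branch applies.** Differences of small counts are far from normal. Shapiro-Wilk rejected in 100% of these runs, so the signed-rank test is the one to expect.

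**3. ANOVA branch.** With two time points this is a paired t-test. Adding zeros leaves S = Σd and Q = Σd² unchanged:

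- completers: t² = S²(n − 1)/(nQ − S²)
- BOCF: t² = S²(N − 1)/(NQ − S²)

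Put r = S²/Q = n·t²/(n − 1 + t²), with t from the completers. For n = 145 and t = 1.977, r = 145 × 3.909/147.909 = 3.832. BOCF t² = 3.832 × 241/238.168 = 3.877, so t = 1.969 and p goes from 0.0500 to 0.0501. For t = 5, r = 145 × 25/169 = 21.45 and t becomes 4.84. In the 12 scenarios the largest loss was 2 of 378 significant results.

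**4. Other zero rules.** With a weak effect (0.6 to 0.47 or 0.50), Pratt ranking lost 8 of 398 (2%) to 36 of 277 (13%) of significant results, and splitting the zeros lost 15 of 368 (4%) to 89 of 245 (36%). With a strong effect (1.2 to 0.2) neither lost any.

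**5. The BOCF estimate does move.** Its mean is (n/N) × the completers' mean. At 40% missing: −0.844 × 145/242 = −0.506. The factor n/N is positive, so the sign cannot change.

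**6. A contrast that can fail.** Give each leaver one relapse more than before baseline (d = +1, for illustration):

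| Assumed pre/post, missing | Primary p | BOCF p | Leavers +1: mean | Leavers +1: p |
|---|---|---|---|---|
| 1.2/0.2, 40% | 3.8e-12 | 3.8e-12 | −0.506 + 97/242 = −0.105 | 0.67 |
| 1.0/0.5, 20% | 1.9e-7 | 1.9e-7 | −0.338 + 48/242 = −0.140 | 0.11 |

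The overall mean reaches zero at delta = −S/(N − n): 0.844 × 145/97 = 1.26 in the first row and 0.422 × 194/48 = 1.71 in the second. The 95% CI includes zero at a smaller delta.

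**7. True overall change of zero (assumed).** Pre 0.9 and completers 0.7. Leavers are then 1.7 at 20% missing (0.8 × 0.7 + 0.2 × 1.7 = 0.90) or 1.37 at 30% (0.7 × 0.7 + 0.3 × 1.37 = 0.90). The completers-only and BOCF signed-rank tests both reject in about 50 to 55% of data sets. With completers at 0.6 they reject in 83 to 91%. With completers at 0.7, Pratt ranking still rejects in 41 to 54%. A delta of 1.0 favours cladribine in 0 to 4%.

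**The case against.** The strongest reply is that BOCF is only one of two checks. LOCF stands in the same section and the same table, and uses the leavers' own earlier on-study ARR. In the zero-change example, if the leavers' higher rate is already visible over one observed year, LOCF signed-rank favoured cladribine in only 3 to 5% of data sets (completers 0.7) or 4 to 8% (0.6). The table would then usually show LOCF disagreeing with the primary result. This stands, with one limit: LOCF misses a worsening that comes after the last recorded visit.

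A reader might infer that the BOCF analysis as a whole cannot fail, or that the plan has no working drop-out check. The documents do not support either. SAP 14.1.2 also prints summary statistics, in which the shrunken mean is visible. LOCF is planned. Exact equality of the p-values rests on a zero rule that the SAP leaves open. SAP 10.1 tabulates discontinuations by reason, and Protocol 9.9 names attrition as a limitation.

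It is also fair to say that the rejection rates in step 7 are the completers-only rates. They show what excluding leavers can do under chosen inputs, not harm that BOCF adds. They depend on the assumed dispersion and pre/post correlation: with completers at 0.7, other settings gave 36 to 58%.

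**Conclusion.** The point holds for the BOCF test result. With zeros dropped, its p-value is the completers-only p-value for any amount of missing data and any outcome of the leavers. That is exact and rests on no assumed rate. In the ANOVA branch the change is negligible. Under Pratt ranking or zero-splitting the p-value can differ, but still takes nothing from what happened to the leavers. A matching BOCF p-value should therefore not be read as support for the primary test.

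The effect is limited. One of two supportive analyses is concerned, and neither the primary estimate nor the primary test changes. The documents give no readable drop-out figure, so how much drop-out matters in this study cannot be judged from them. The zero-change example shows only that a false reassurance is possible. The change should be made before database lock.

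**What to change.** In SAP 14.1.2:

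1. Keep BOCF as an estimate with its 95% CI. Remove its p-value and any statement that it supports the primary test.
2. Keep LOCF.
3. Add a delta (tipping-point) analysis over the Full Analysis Set: missing post-baseline ARR = pre-baseline ARR + delta, on a pre-specified grid (for example 0 to 2.0 relapses/year). Report the mean difference and 95% CI at each delta, and the delta at which the CI first includes zero.
4. Read that delta against the leavers' observed on-study relapse rate. Protocol 9.2.4 already collects relapse counts at visits and, where available, at termination.

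In SAP 14.1.1, state how the signed-rank test treats zero differences.

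The delta analysis has limits of its own. A constant delta is single imputation without imputation uncertainty and sets aside relapses recorded for leavers, hence item 4. A small delta may not be enough: with completers at 0.6 and 20% missing, delta 0.5 still favoured cladribine in about 45% of zero-change data sets and delta 1.0 in about 4% (up to 6% under other dispersion settings). The whole grid should therefore be shown.

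Cost: SAP wording and one extra table from data already collected. The robustness statement may become less favourable.

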### 14.1.3 Subgroup Analyses of the Primary Outcome ARR

The subgroup analyses will be performed on the primary endpoint assessment based on the FAS for all subgroup levels defined in IAP Section 8.2 "Subgroup definition and parametrization". All the subgroup analyses are exploratory and will be performed unstratified. No adjustment for multiplicity will be performed. Sensitivity analysis will not be performed in the subgroup analysis.

A forest plot will be presented with the 95% CIs for the difference in ARR between pre and post-baseline for each subgroup for the analysis of the primary outcome. A line plot by subgroup with ARR over time (from Baseline to Visit 4) with means and 95% CIs for ARR at each visit will be presented.

## 14.2 Secondary Outcome ARR

One of the secondary outcomes for this study is the difference in ARR between the pre-baseline 12-month period and over the 12 months period after the start of cladribine (1 year)

Relapses will be diagnosed by the treating physicians, as per routine clinical practice; a typical definition within this context is the appearance of new symptoms or the exacerbation of pre-existing symptoms that are attributed to MS and occur over a minimum of 24 hours and separated from a previous attack by at least 30 days, in the absence of fever or infection.

## 14.2.1 Secondary Objective: Derivation and analysis of the Secondary Outcome ARR

#### **Derivations**

Pre-baseline ARR will be defined as the total number of relapses reported in the last 12 months prior to Cladribine treatment as collected in the "12 Month Historical MS Data".

Twelve month period after the start of Cladribine treatment ARR will be calculated as the sum of the number of MS relapses from Visit 1 and Visit 2 divided by the number of days between Visit 2 data and start date of Cladribine and multiplied by 365.25. If a patient discontinues the study prior to Visit 2, it will be set to missing and excluded from the primary analysis.

#### **Analysis methods**

No missing data imputation will be performed. Patients with missing data at one or both time points will not be included in the analysis. A one-way Repeated Measures ANOVA will be used to compare the differences between pre and post-baseline ARR if the data is normally distributed. The two-tailed test hypothesis for the primary outcome is H0: ARR mean difference between pre and post-baseline ARR is 0 vs H1: ARR mean difference between pre and post-baseline is different than 0. Statistical significance will be assessed at the 5% level.

In case the data is not normally distributed, Wilcoxon signed-rank test will be used instead. The Shapiro-Wilk test will be used to test for data normality.

## 14.2.2 Sensitivity Analyses of the Secondary Outcome ARR

No sensitivity analysis will be performed on the secondary outcome analysis.

### 14.2.3 Subgroup Analyses of the Secondary Outcome ARR

The subgroup analyses will be performed on the secondary outcome assessment based on the FAS for all subgroup levels defined in IAP Section 8.2 "Subgroup definition and parametrization". All the subgroup analyses are exploratory and will be performed unstratified. No adjustment for multiplicity will be performed.

A forest plot will be presented with the 95% CIs for each subgroup for the analysis of the secondary outcome.

## 14.3 Secondary Outcome 6-month Disability Progression

The percentage of patients with 6-month disability progression at the end of the study follow-up period (2 years), measured as EDSS, timed 25-foot walk (T25FW) (optional) and 9-hole peg test (9-HPT) (optional) is a secondary outcome of this study.

Disability progression is defined as progression on  $\ge 1$  of 3 components (EDSS, T25FW, and/or 9HPT) confirmed  $\ge 24$  weeks apart and with a  $\ge 20\%$  minimum threshold change for T25FW and 9HPT. Progression on EDSS is defined as at least 1 point in the EDSS score or an increase of at least 1.5 points if the baseline EDSS score is 0.

# 14.3.1 Secondary Objective: Derivation and analysis of the Secondary Outcome 6-month Disability Progression

#### **Derivations**

Disability progression will be assessed using the Visit 4 data and comparing the results with Visit 3. As per definition, if Visit 4 and Visit 3 dates are not separated by at least 24 weeks, disability progression will be set to missing. Disability progression will be assessed if at least one assessment (EDSS, T25FW or 9HPT) is available. As per definition, disability progression will be derived as "Yes" if at least one of the below cases occur:

- Visit 4 EDSS is ≥1 point greater than Visit 3 EDSS if Visit 3 EDSS is greater than 0;
- Visit 4 EDSS is 1.5 or greater when Visit 3 EDSS is 0;
- 20% increase in the T25FW score (average of the two trials) from Visit 3 to Visit 4;
- 20% increase in the 9HPT score (The two trials for each hand are averaged, converted to the reciprocals of the mean times for each hand and then the two reciprocals are averaged) from Visit 3 to Visit 4.

If none of those cases occurred, disability progression will be set to "No".

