8.2 Secondary Objectives

- To assess change in annualized relapse rate (ARR) in patients switching from first-line DMDs to Cladribine tablets, between the 12-month pre-baseline period and over the 12 months period after initiation of Cladribine tablets (1 year)
- To assess disability progression. Disability progression is defined as progression on ≥1 of 3 components (EDSS, T25FW, and/or 9HPT) confirmed ≥24 weeks apart and with a ≥20% minimum threshold change for T25FW and 9HPT. T25FW and 9HPT are optional and will be performed if done as per routine practice. Progression on EDSS is defined as at least 1 point in the EDSS score or an increase of at least 1.5 points if the baseline EDSS score is 0.
- To assess disability improvement. Disability Improvement is defined as improvement on ≥1 of 3 components (EDSS, T25FW, and/or 9HPT) confirmed ≥24 weeks apart and with a ≥20% minimum threshold change for T25FW and 9HPT. T25FW and 9HPT are optional and will be performed if done as per routine practice. Improvement on EDSS is defined as a decrease in EDSS by at least 1 point (1.5 points if baseline EDSS was 1.5).
- To assess safety of Cladribine tablets in the real world, at two years
- To assess Quality of Life and treatment satisfaction
- To assess treatment adherence

-

Exploratory Objectives

- For those patients that the treating physicians decide to prescribe an MRI at baseline and/or Year 2:
 - 1. To compare MRI characteristics between baseline and Years 1 and 2
 - To compare MRI characteristics between the 12-month pre-baseline and postbaseline results (Years 1 and 2)
- To study effectiveness in 5 subgroups, defined according to the pre-baseline DMD treatment (IFN- B 1a / IFN- B 1 B / Glatiramer Acetate, Teriflunomide, DMF).

L04AA40 MS700568_0070	Cladribine	
9	Research Methods	
9.1	Study Design	
9.1.1	Design Overview	

This is a prospective, non-interventional, multicenter, Phase IV study in patients with a confirmed diagnosis of RRMS who switched from first-line DMD treatment (Interferons, Glatiramer Acetate, Teriflunomide, DMF) to treatment with Cladribine tablets in routine clinical practice.

No study specific interventions will be performed on the patients and there will not be any study specified visits. Assessments planned in this protocol will be according to clinical practice.

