9.1.2.2 Secondary

- Difference in ARR between the pre-baseline 12-month period and over the 12 months period after the start of cladribine (1 year)
- Percentage of patients with 6-month disability progression⁵ at the end of the study followup period (2 years), measured as EDSS, T25FW (optional) and 9-HPT (optional).

⁴ Relapses will be diagnosed by the treating physicians, as per routine clinical practice; a typical definition within this context is the appearance of new symptoms of the exacerbation of pre-existing symptoms that are attributed to MS and occur over a minimum of 24 hours and separated from a previous attack by at least 30 days, in the absence of fever or infection.

⁵ Disability progression is defined as progression on ≥1 of 3 components (EDSS, T25FW, and/or 9HPT) confirmed ≥24 weeks apart and with a ≥20% minimum threshold change for T25FW and 9HPT, Progression on EDSS is defined

L04AA40 MS700568 0070

Cladribine

- Percentage of patients with 6-month disability improvement⁴ at the end of the study followup period (2 years), measured as EDSS, T25FW (optional) and 9-HPT (optional)
- · Occurrence of adverse events and of serious adverse events
- Quality of life (MSIS-29)
- Treatment Satisfaction (TSQM v1.4)
- CCI
- Treatment adherence, assessed as percentage of cladribine tablets taken versus prescribed dose

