#### **Analysis methods**

No missing data imputation will be performed. The proportion of patients with 6-month disability progression at the end of study will be presented including associated 95% Clopper Pearson exact intervals.

Disability progression at Visit 1, Visit 2 and Visit 3 will also be presented and derived in the same way. A bar plot with disability progression from Visit 1 to Visit 4 will be presented. Additionally, the results for EDSS, 9HPT and T25FW scores will be presented descriptively by Visit, including an absolute and relative change from baseline and to the previous visit.

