### 14.4 Secondary Outcome 6-month Disability Improvement

The percentage of patients with 6-month disability improvement at the end of the study follow-up period (2 years), measured as EDSS, T25FW (optional) and 9-HPT (optional).

Disability Improvement is defined as an improvement on  $\geq 1$  of 3 components (EDSS, T25FW, and/or 9HPT) confirmed  $\geq 24$  weeks apart and with a  $\geq 20\%$  minimum threshold change for T25FW and 9HPT. Improvement on EDSS is defined as a decrease in EDSS by at least 1 point (1.5 points if baseline EDSS was 1.5).

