# 14.4.1 Secondary Objective: Derivation and analysis of the Secondary Outcome 6-month Disability Improvement

#### **Derivations**

Disability improvement will be assessed using the Visit 4 data and comparing the results with Visit 3. As per definition, if Visit 4 and Visit 3 dates are not separated by at least 24 weeks, disability improvement will be set to missing. Disability improvement will be assessed if at least one assessment (EDSS, T25FW or 9HPT) is available. As per definition, disability improvement will be derived as "Yes" if at least one of the below cases occur:

- Visit 4 EDSS is ≥1 point smaller than Visit 3 EDSS if Visit 3 EDSS is greater than 1.5;
- Visit 4 EDSS is 0 when Visit 3 EDSS is 1.5;
- 20% decrease in the T25FW score (average of the two trials) from Visit 3 to Visit 4;
- 20% decrease in the 9HPT score (The two trials for each hand are averaged, converted to the reciprocals of the mean times for each hand and then the two reciprocals are averaged) from Visit 3 to Visit 4.

If none of those cases occurred, disability improvement will be set to "No".

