#### **Analysis methods**

No missing data imputation will be performed. The proportion of patients with 6-month disability improvement at the end of study will be presented including associated 95% Clopper Pearson exact intervals. Disability improvement at Visit 2 and Visit 3 will also be presented and derived in the same way as described for Visit 4.

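### SAP 14.3.1 and 14.4.1 score 2-year disability progression and improvement as unconfirmed Visit 4 versus Visit 3 change, although the definition requires confirmation and keys the special EDSS thresholds to baseline

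*SAP*

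**What the plan says.** **Definition.** Protocol 8.2, repeated in SAP 14.3 and 14.4, defines progression or improvement as a change on at least one of EDSS, T25FW and 9HPT, confirmed at least 24 weeks apart, with a 20% minimum for the two timed tests. For EDSS the general rule is 1 point. The exceptions refer to baseline: for progression, "an increase of at least 1.5 points if the baseline EDSS score is 0"; for improvement, "1.5 points if baseline EDSS was 1.5". SAP 9.1 defines baseline as the last value before the first dose, or the Baseline-visit value for patients enrolled after dosing.

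**Derivation.** SAP 14.3.1 states: "Disability progression will be assessed using the Visit 4 data and comparing the results with Visit 3". SAP 14.4.1 matches it: "Disability improvement will be assessed using the Visit 4 data and comparing the results with Visit 3". The special EDSS rules are applied when Visit 3 EDSS is 0 (progression) or 1.5 (improvement). The 24 weeks appear only here: "if Visit 4 and Visit 3 dates are not separated by at least 24 weeks, disability progression will be set to missing".

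**Other visits.** For progression: "Disability progression at Visit 1, Visit 2 and Visit 3 will also be presented and derived in the same way". For improvement: "Disability improvement at Visit 2 and Visit 3 will also be presented and derived in the same way as described for Visit 4". The improvement bar plot in SAP 14.4.3 and the interim outputs in SAP 18.2 nevertheless include improvement at Visit 1.

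**Declared changes.** SAP 7 declares no change from the protocol analyses.

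**The concern.** A confirmed change needs three scores on a component: a reference, a score that meets the threshold, and a later score that still meets it. The SAP derivation uses two. Visit 3 becomes the reference, and the 24 weeks stop being a confirmation period and become the interval over which change is measured. A 6-month status at Visit 1 shows the same gap, because a patient then has one post-baseline score and nothing to confirm it with.

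At stake is the meaning of two reported percentages. They would be labelled 6-month disability progression and improvement at 2 years, but would describe unconfirmed change from about month 18 to month 24. Disability progression is part of the study's stated main aim, and the same rule feeds the sensitivity, subgroup and interim outputs.

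**Working it through.** **1. No plan figure to reproduce.** The documents state no expected disability rate and no power for these endpoints.

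**2. Worked EDSS cases (no assumptions needed).** The SAP column applies SAP 14.3.1 or 14.4.1 literally.

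| EDSS at baseline, V1, V2, V3, V4 | SAP rule at Visit 4 | Against the definition |
|---|---|---|
| 2, 4, 4, 4, 4 | V4 − V3 = 0: not progressed | 2 points above baseline at all four visits |
| 2, 2, 2, 2, 3 | V4 − V3 = 1: progressed | first seen at Visit 4, not confirmed |
| 2, 2, 2, 4, 3 | V3 − V4 = 1, V3 above 1.5: improved | 1 point worse than baseline |
| 1, 1, 1, 0, 1.5 | V3 = 0, V4 = 1.5: progressed | 0.5 above a baseline of 1 |

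**3. Does another passage repair this?** Protocol 9.7.3 asks for sequential values at 6-month intervals, which sets spacing only. The four sensitivity analyses in each of SAP 14.3.2 and 14.4.2 vary missing-data handling, the component used and proximity to relapse; all keep the two-score rule. None restores the baseline reference or the confirmation.

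**4. Illustration of size.** These are assumptions, not document figures: EDSS progression only, one permanent 1-point step at rate *h* per year, no rating error, visits at 0, 6, 12, 18 and 24 months. Confirmed progression requires the step by month 18. The SAP rule counts steps between months 18 and 24.

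- Confirmed = 1 − exp(−1.5*h*). SAP rule = exp(−1.5*h*) − exp(−2*h*).
- *h* = 0.05: 1 − 0.928 = 7.2%; 0.928 − 0.905 = 2.3%.
- *h* = 0.10: 1 − 0.861 = 13.9%; 0.861 − 0.819 = 4.2%.

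In this model the two rules pick out different patients altogether.

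**5. The direction is not fixed.** A simulation from baseline EDSS 2.0 took repeat steps at 2% per year, a rating error of +0.5 and of −0.5 in 10% of readings each, and a transient +1 with probability 0.10 at each post-baseline visit. Change confirmed at any time up to Visit 4 was about 5.2%, change present at Visit 3 and confirmed at Visit 4 about 3.4%, and the SAP rule 8.9%. Over 36 assumed scenarios the SAP rule gave 0.30 to 1.71 times the first reading and counted 0 to 12% of confirmed progressors. These ranges are not bounds.

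**6. Short gaps.** SAP 9.5 has no visit windows for this endpoint. If its PRO windows are borrowed (days 510–570 and 700–760, uniform and independent), the Visit 3 to Visit 4 gap runs from 130 to 250 days. The share below 168 days is (168 − 130)² / (2 × 60²) = 1444 / 7200 = 20%. Any revised rule must therefore say how such patients are classed.

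**The case against.** The best defence is that the protocol invites the SAP rule. Protocol 9.7.3 is its only methods sentence on how these values enter the analysis, and it speaks of sequential values six months apart. The general 1-point and 20% rules name no reference visit. This stands in part. A reader might infer that the protocol expressly requires all change to be measured from baseline; it does not. Baseline is named only in the EDSS exceptions, so a baseline reference throughout is the natural reading rather than explicit text. Two conflicts remain firm: the exceptions have moved from baseline to Visit 3, and the confirmation has no operation. The spacing sentence fits a baseline change confirmed at the next visit equally well and does not remove confirmation.

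A second defence is that little is lost. SAP 14.3.1 also presents progression status at the earlier visits and the scores by visit with change from baseline, so early worsening is visible where it occurs. That also stands: the harm is a mislabelled headline percentage, not missing information.

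Two further inferences go too far. One is that the SAP rule always understates progression; step 5 shows that it can overstate it. The other is that the change was made knowingly. SAP 14.3.1 says that it follows the definition, which is consistent with a misreading.

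**Conclusion.** The derivation is wrong as written. It departs from the SAP's own definition on confirmation and on the reference for the special EDSS thresholds, and SAP 7 does not declare this. The worked cases establish misclassification in both directions without any assumption. Size and direction cannot be stated from the documents: 7.2 to 13.9% against 2.3 to 4.2% rests on an assumed 5 to 10% yearly rate of one permanent EDSS step without rating error, and nothing comparable has been worked out for improvement or for an expected effect in this study.

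The protocol also leaves open whether 2-year status means change confirmed at any time or change present at the end. The documents do not settle this, so neither reading can be called the required one; the SAP rule matches neither. Nor can the point be extended to the main result: SAP 9 confines confirmatory testing to the primary outcome, and the ARR analysis does not use these scores. It should be corrected before database lock.

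**What to change.** In SAP 14.3.1 and 14.4.1:

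- For each component, derive change from baseline as defined in SAP 9.1, with the EDSS 0 and 1.5 rules keyed to baseline EDSS. Require the threshold to be met at a post-baseline visit and still met on the same component at the next assessment at least 24 weeks later.
- State one headline reading, either confirmed at any time up to Visit 4, or present at Visit 3 and confirmed at Visit 4. Report the other as a sensitivity analysis.
- Under the first reading, keep as Yes any patient confirmed before leaving.
- Set to missing, not No, any patient without confirmed change whose status cannot be determined because baseline is missing, the confirming gap is under 24 weeks, or follow-up ended early. Show these counts, with patients withdrawn for a DMD switch (Protocol 9.2.5) listed separately.
- Align SAP 14.3.2, 14.3.3, 14.4.2, 14.4.3 and 18.2, and show no confirmed status at Visit 1. Keep visit-to-visit change as a descriptive table.

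**Cost.** SAP wording and programming. EDSS is already scheduled at baseline and all four visits, so no new collection is needed. The small downside is that the optional T25FW and 9HPT would need baseline plus two later values instead of two values, so more of them will be missing.

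**Minimum alternative.** Rename the endpoints as unconfirmed change from month 18 to month 24 and declare this in SAP 7.
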